PMID: 26283834: Zakine et al. [49] performed a double-blinded study comparing the effectiveness of ketamine administration in two different settings with one control group which received placebo. The first ketamine group received a 0.5 mg/kg bolus perioperatively and a 2 µg/kg/min infusion thereafter for 48 hours; the second ketamine group received a 0.5 mg/kg bolus perioperatively and a 2 µg/kg/min infusion only for the duration of the surgical procedure. All of the patients were given morphine PCA. The authors found that cumulative morphine consumption was significantly lower in the group receiving the 48-hour infusion when compared to the shorter infusion and control groups. VAS scores were measured postoperatively and were significantly lower in the ketamine groups when compared to the control group. As an added effect, while all patients in the study received hydroxyzine preoperatively, the 48-hour infusion group experienced significantly less nausea than the control group (4% versus 27%, ). It is worth noting that there were no side effects of the ketamine, psychotomimetic, or otherwise.

PMID: 23814653: Hadi et al. [40] used low-dose IV ketamine as an adjunct to therapy during and after lumbar microdiscectomy surgery. Patients were divided into a control group, a group receiving 1 µg/kg/min perioperatively and a group receiving both 1 µg/kg/min perioperatively and 1 µg/kg/min postoperatively. The patients in the control group required first analgesic demand dose earlier than the ketamine groups. Total morphine consumption, visual analog scale (VAS) pain scores, and rates of nausea and vomiting were significantly lower in the group receiving both peri- and postoperative ketamine versus the control group.

PMID: 22374377: Suppa et al. [48] performed a similar study in women undergoing elective Cesarean sections, using a 0.5 mg/kg ketamine bolus 10 minutes after birth in addition to a 2 µg/kg/min IV ketamine infusion for 12 hours thereafter. Usage of ketamine reduced morphine requirements at the 4–8, 8–12, and 12–24-hour time points. The patients in the ketamine group showed reduced pain sensitivity at the T-10 dermatome, suggesting an antihyperalgesic effect. At three years after surgery, patients reported no differences in residual pain or dysesthetic symptoms.

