## **12. Statistical considerations including sample size justification (power analysis) and statistical analysis plan (optional at this stage for investigators not versed in statistical methodology):**

This study is a cluster randomized, pragmatic clinical trial. Initial analysis will use descriptive statistics and data visualizations to both identify and address spurious values, and to characterize the study cohort. Characteristics will be grouped by study arm, but we do not plan to compare the study arms with statistical tests.

The primary outcome is length of stay, measured in days. It is expected that length of stay is a skewed distribution, and so non-parametric methods are preferred. However, it

is not possible to consider the clustering or baseline covariates using a Wilcoxon test. Therefore, a proportional odds regression model will be used. Clustering will be taken into account using a mixed-effects model. If there are patients included twice because they underwent two elective major abdominal surgeries, patient will also be included as a random effect. The model will include baseline characteristics such as age, BMI, history of substance use (smoking status and opioid status if available), and type of surgical procedure. The common odds ratio from the model will be estimated; this quantity can be interpreted similar to the concordance probability and is robust to the proportional odds assumption. We will also report the model-assisted estimands of mean and median length of stay. Bootstrapping will be used to generate appropriate confidence intervals.

We will use an intention to treat analysis and all participants who are randomized will be included in the statistical analysis and analyzed according to group assignment. Participants will be removed from the analysis if their provider deems the patient ineligible prior to study drug administration. If a participant or provider withdraws the participant from the study following study drug administration, the participant will receive care at the provider's discretion, but will remain in the statistical analysis.

The secondary outcomes will be explored in a similar way. The proportional odds model will be used to evaluate differences in opioid use in the hospital. Occurrence of events will be reported as rates with confidence intervals. Logistic regression will be used to compare the odds of events between groups.

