 - b. Mild side effects, but prefers discontinuation
 - c. Debilitating hallucinations
 - d. Debilitating dizziness
 - e. Hemodynamic instability
 - f. Other severe side effect

4. The incidence of ileus requiring gastric decompression as defined by orogastric or nasogastric tube placement in the postoperative period

Exploratory Outcomes

1. Instances of reoperation within the index encounter
2. VUMC hospital readmissions within 30 days post-discharge (not including ED visits)

Design Considerations

Randomization

Randomization will occur in clusters of one week. All patients in the same week will receive the same therapy (ketamine or placebo), with the selection being determined by a pre-generated random sequence.

Power and Sample Size

We anticipate the use of ketamine will reduce LOS following surgery start. To determine how long this trial will need to run to have sufficient power to detect a meaningful difference, we assumed 85% power, a type I error rate of 5%, and a 10% reduction in LOS. We estimated the within period correlation from preliminary data concerning the length of stay for major abdominal surgeries to be about 0.014. Given these assumptions, about 1514 patients would need to be included overall. An increase in sample size is necessary to accommodate for the two post-randomization exclusions that are pre-specified. We expect approximately 30 participants to be impacted by these post-randomization exclusions and will therefore increase the sample size by 30 to account for this exclusion (n=1544). Given surgical volumes, we expect 20 patients to be enrolled each week, and for the trial to last approximately 18 months.

Statistical Approach

Descriptive Analysis

We will describe the study cohort both overall and by treatment arm. To characterize the study sample, demographic and clinical data will be described. Categorical variables will be described using frequencies and proportions; continuous variables will be described using means and standard deviations as well as medians and interquartile ranges (IQR). Missingness will be recorded for each variable. To further assess the distribution of variables, graphical summaries will be displayed using graphs such as boxplots, dotplots, and/or histograms. No statistical testing will be performed to compare characteristics between groups. At a minimum, the following baseline variables will be described:

- Age (years)
- Sex assigned at birth (male, female, unknown)
- Race
 - Caucasian

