Secondary analyses: The secondary outcomes will be analyzed with the same covariates. A mixed-effect proportional odds model will be used to evaluate difference in opioid use in the hospital between the intervention and placebo arms. For each of the binary outcomes, a mixed-effect logistic regression will be used to compare the odds of events between the two arms.

Exploratory analyses: The exploratory outcomes will be presented in tables comparing the incidences of reoperation and hospital readmission within 30 days post-discharge between two arms.

Differential Treatment Effects

Differential treatment effects will be explored by examining the interaction between the treatment indicator and each variable that potentially interacts with treatment, one variable at a time, but subgroup analysis will not be performed. The variables we consider include sex, opioid naïve status, type of surgical procedure (colorectal, ventral hernia, or surgical oncology), epidural vs. truncal nerve block, known history of depression, and known history of PTSD.

References

5. Mercadante S. Opioid Analgesics Adverse Effects: The Other Side Of The Coin. *Curr Pharm Des.* 2019;25:1-6. doi:10.2174/1381612825666190717152226.

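### Does the SAP need a stated fallback for a binary secondary outcome with no events in one arm, or for a logistic model that does not converge?

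*SAP*

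**What the plan says.** The Secondary analyses paragraph of the SAP gives one method: "For each of the binary outcomes, a mixed-effect logistic regression will be used to compare the odds of events between the two arms". It adds: "The secondary outcomes will be analyzed with the same covariates". That carries over the primary model's eleven named covariates, with continuous ones as cubic splines, and week is a random effect in that model. There is no condition on the number of events and no step for a failed fit. The only if-then rule for the models, under Primary analysis, concerns missing covariates.

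The outcomes most likely to be sparse are in item 3 of Secondary Outcomes, which lists six documented reasons for stopping the infusion early. Five of them (b to f) are side effects or instability, for example "Debilitating hallucinations".

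Protocol section 12 adds a descriptive commitment, "Occurrence of events will be reported as rates with confidence intervals", and then the comparison, "Logistic regression will be used to compare the odds of events between groups". It also puts effect sizes ahead of p-values, mentions bootstrap confidence intervals for the primary model, and says the secondary outcomes will be handled in a similar way.

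The two exploratory outcomes do not raise the question, since they are only tabulated: "The exploratory outcomes will be presented in tables comparing the incidences of reoperation and hospital readmission within 30 days post-discharge between two arms".

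**The concern.** If one arm has no events, the maximum-likelihood odds ratio does not exist as a finite number. It is infinite when placebo is empty and 0 when ketamine is empty. It is also the only between-arm effect that either document names for these outcomes, so the preferred summary would be missing where an imbalance is most extreme.

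Splitting early cessation into single reasons makes an empty cell more likely. Protocol section 5 describes a trial with a 48-hour infusion in these terms: "It is worth noting that there were no side effects of the ketamine, psychotomimetic, or otherwise". Very low counts are therefore conceivable.

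The stake would be the reading of a harm. If the method is chosen after the counts are known, one analyst could report a Wald p-value near 1 and another a likelihood-ratio p-value below 0.01 from the same data.

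**Working it through.** **Inputs.** The SAP's Power and Sample Size section gives 1514 analysed patients. The allocation ratio is not stated; 1:1 is assumed, giving 1514/2 = 757 per arm. No event rates are given, so every rate below is an assumption. The plan states no figure on this point to reproduce.

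**1. How likely is an empty arm?** With independent patients, P(no events in a given arm) = (1 − p)^757. With equal rates, P(at least one arm empty) = 1 − (1 − that)².

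| True rate p | Expected events per arm | Given arm empty | At least one arm empty |
|---|---|---|---|
| 0.1% | 0.76 | 47% | 72% |
| 0.2% | 1.51 | 22% | 39% |
| 0.5% | 3.79 | 2.2% | 4.5% |
| 1% | 7.57 | 0.05% | 0.1% |

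For reasons b to f together, allow one reason per patient and use inclusion–exclusion over the five categories. The chance that at least one is empty on placebo is:

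| Total placebo rate, b to f | Split evenly | Split 40/30/15/10/5 |
|---|---|---|
| 1% | 71% | 90% |
| 2.5% | 11% | 51% |
| 5% | 0.25% | 17% |

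The answer depends almost wholly on a rate that the documents do not give.

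**2. What would the model print?** An unadjusted logistic fit to 0/757 against 3, 5 or 8/757 gives a log odds ratio of 21 to 22 with a standard error of about 12,944. The software reports convergence, but nobody would mistake this for a usable estimate.

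**3. How far apart are the candidate tests?** For x ketamine events against 0, the unadjusted likelihood-ratio statistic is 2{x ln(x/757) + (757 − x) ln(1 − x/757) − x ln(x/1514) − (1514 − x) ln(1 − x/1514)}. For x = 6 this is 8.34 (p = 0.0039); for x = 8 it is 11.13 (p = 0.0008). Fisher's exact p-values are 0.031 and 0.0077. The Wald p-value is 0.999.

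The planned type of model was also fitted, with a random week intercept and 22 fixed effects, to 100 simulated data sets with 6, 8, 10 or 15 ketamine events against 0. Wald p ran from 0.15 to 1.00 and likelihood-ratio p was at most 0.0099. The likelihood-ratio figure is somewhat flattering: under no effect, with 22 fixed effects and no random intercept, that test rejected in 6.5% to 8.2% of data sets at a nominal 5%.

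Only the Wald test hides the imbalance, and neither document specifies it.

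**4. What would the reader see anyway?** The promised rates would show 6/757 = 0.79% against 0/757 = 0%. The exact 95% upper limit for the empty arm is 1 − 0.025^(1/757) = 0.49%, ignoring clustering.

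**5. Would a pre-named fallback be clearly better?** Take the candidate of an unadjusted risk difference with a Newcombe interval, dividing counts and arm sizes by a design effect 1 + (m − 1) × ICC. The ICC available is the one in the SAP: "We estimated the within period correlation from preliminary data concerning the length of stay for major abdominal surgeries to be about 0.014". It was estimated for length of stay, not for events.

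- At 15 patients per week the design effect is 1 + 14 × 0.014 = 1.20. Then 6 against 0 gives 0.79 percentage points (0.04 to 1.84), and 8 against 0 gives 1.06 (0.24 to 2.20).
- At 20 per week it is 1 + 19 × 0.014 = 1.27, and the lower limit for 6 against 0 falls to 0.00.
- In simulation (6000 trials per scenario) overall coverage was 96% to 99.9% at an ICC of 0 or 0.014, and 92% to 98% at 0.05. Among trials that would trigger the fallback, it fell to 82% to 84% when both arms had a true rate of 0.5%.

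So for the borderline count the result turns on an assumed ICC and cluster size.

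**The case for a change.** The strongest case for a change is that one sentence costs almost nothing and removes a choice made after the counts are seen, on outcomes that concern harm. It is also true that the promised rates describe each arm separately and do not supply a between-arm effect, and that bootstrapping would not help, since resampling an arm with no events returns no events. Because software can report convergence with an empty arm, a check on convergence alone would not catch the problem. All of this stands.

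It does not carry the point further, for four reasons. First, the misreading requires an analyst to report a Wald test that the plan does not name, ignore an absurd standard error, and omit rates that the protocol promises. Second, item 3 can be read as one categorical record of why the order was stopped, to be tabulated, in which case five separate regressions never arise; the SAP is not explicit. Third, the blinded placebo patients receive other analgesics, and the consent wording in Protocol section 7 lists confusion, agitation and blood-pressure changes among the side effects of pain medicines. Some placebo stops are therefore plausible. Fourth, the risk-difference rule would report 8 against 0 as an unadjusted difference and 8 against 1 from a model with some 22 coefficients, leaving overfitting with few events untouched. Applied to any non-convergence, it would also discard covariate adjustment where a smaller covariate set might have solved the problem. No non-convergence rate has been shown.

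**Conclusion.** The gap exists, but it is one that analysts fill sensibly, and no change to the plan is called for. With an empty arm, a competent analyst would give counts and rates and either a penalised or likelihood-based odds ratio from the planned model or a risk difference allowing for weeks. With a failed fit, the first step would be to simplify the covariates. These are choices among reasonable methods, and the risk-difference option examined here has weaknesses of its own.

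The exposure is small. An empty arm is realistic only for an outcome at about 0.5% or less in that arm (2.2% chance at 0.5%, 0.05% at 1%), assuming 757 per arm, independent patients and rates that the documents do not state. Outcomes with events in both arms and a converging model, the primary analysis and the sample size are unaffected. The conclusion rests on the protocol's commitment to report rates with confidence intervals being honoured, although the SAP does not repeat it.
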